7.3 Labelling

Labels will be prepared in accordance with Good Manufacturing Practice (GMP) and local regulatory guidelines. The labels will fulfil GMP Annex 13 requirements for labelling. Label text will be translated into local language.

7.4 Storage

All study drugs should be kept in a secure place under appropriate storage conditions. The investigational product label on the bottle specifies the appropriate storage.

7.5 Compliance

The administration of all study drugs should be recorded in the appropriate sections of the Case Report Form.

Patients should return all unused medication and empty containers to the investigator.

7.6 Accountability

The study drug provided for this study will be used only as directed in the study protocol.

The study personnel will account for all study drugs dispensed to and returned from the subject.

The study personnel at the investigational site will account for all drugs dispensed and for appropriate destruction. Certificates of delivery and destruction should be signed.

7.7 Concomitant and other treatments

Information on any treatment in the 4 weeks prior to starting study treatment and all concomitant treatments given during the study, with reasons for the treatment, will be recorded in the Case Report Form (CRF). Guidance on medications that require close monitoring is given in Section 3.5 and [Appendix F](#).

Prohibited Medication/Class of drug:	Usage:
Other anticancer agents, investigational agents and radiotherapy	Should not be given while the patient is on study treatment.

Rescue/Supportive Medication/Class of drug:	Usage:
Pre-medication will be allowed after, but not before the first dose of study treatment.	To be administered as directed by the investigator. This includes management of diarrhoea, nausea and vomiting.
Blood transfusions	Allowed at any time during the study.
Granulocyte colony stimulating factors	Should not be used prophylactically during Cycle 1. Use of prophylactic colony stimulating factors may be considered after Cycle 1 following discussion with the AstraZeneca Study Team Physician.
Corticosteroids and/or bisphosphonates	Patients may receive treatment with corticosteroids and/or bisphosphonates for the treatment of bone metastases.
Palliative radiation	Patients may receive radiotherapy for painful bony metastases.
Supportive care and other medications that are considered necessary for the patient's well-being	To be administered as directed by the investigator.

7.7.1 Other concomitant treatment

Other medication other than that described above, which is considered necessary for the subject's safety and well being, may be given at the discretion of the Investigator and recorded in the appropriate sections of the Case Report Form.

7.8 Post study access to study treatment

Patients receiving AZD9291 at the time of study completion (i.e. after final data cut-off date) may continue to receive AZD9291, if in the opinion of their treating physician they are continuing to derive clinical benefit from continued treatment. Such patients will continue to be monitored and all safety assessments will be performed until AZD9291 is discontinued. These patients will then be followed up for a period of 28 days after the last AZD9291 dose is administered for any new treatment-related serious adverse events. A CSR addendum will be prepared to summarise any additional safety data collected.

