6.3 Recording of adverse events

6.3.1 Time period for collection of adverse events

Adverse Events will be collected from time of signature of informed consent throughout the treatment period and including the safety follow-up period. The follow-up period is defined as 28 days after study treatment is discontinued. SAEs occurring in the follow-up period should be reported to AstraZeneca in the usual manner (see Section [6.4](#)).

Following discontinuation of AZD9291, SAEs considered related to study procedures should continue to be collected as outlined in [Table 8](#).

After the final database lock, there may be some patients remaining on study treatment. For these patients who are continuing to receive AZD9291 AstraZeneca will collect information (during the treatment period and for 28 days after last dose) on SAEs, deaths (including those due to disease progression), discontinuation due to AEs/SAEs and drug accountability only.

Table 8 Summary of recording and follow-up of adverse events and deaths

	Consent to Treatment Period	Until 28-day Follow-up Visit (safety follow-up period)	Post 28-day Follow-up visit but prior to progression (if applicable)	Post 28-day Follow-up visit and post progression (survival follow-up period)
Collect all new AEs in CRF	Yes	Yes	No	No
Collect all ongoing AEs in CRF	Yes	Yes	Yes	Yes
Collect all study procedure-related SAEs in CRF	Yes	Yes	Yes	Yes
Death due to AE, or unknown cause¹	Yes	Yes	No	No

¹ for example, death not due to disease progression, refer to Section [6.3.10](#)

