6.4 Reporting of serious adverse events

All SAEs have to be reported, whether or not considered causally related to the investigational product, or to the study procedure(s). All SAEs will be recorded in the CRF.

If any SAE occurs in the course of the study, then Investigators or other site personnel inform the appropriate AstraZeneca representatives within one day i.e., immediately but **no later than 24 hours** of when he or she becomes aware of it.

The designated AstraZeneca representative works with the Investigator to ensure that all the necessary information is provided to the AstraZeneca Patient Safety data entry site **within 1 calendar day** of initial receipt for fatal and life threatening events **and within 5 calendar days** of initial receipt for all other SAEs.

For fatal or life-threatening adverse events where important or relevant information is missing, active follow-up is undertaken immediately. Investigators or other site personnel inform AstraZeneca representatives of any follow-up information on a previously reported SAE within one calendar day i.e., immediately but **no later than 24 hours** of when he or she becomes aware of it.

Once the Investigators or other site personnel indicate an AE is serious in the WBDC system, an automated email alert is sent to the designated AstraZeneca representative.

If the WBDC system is not available, then the Investigator or other study site personnel reports a SAE to the appropriate AstraZeneca representative by telephone.

The AstraZeneca representative will advise the Investigator/study site personnel how to proceed.

The reference document for definition of expectedness is the IB for the AstraZeneca drug AZD9291 and the EU Summary of Product Characteristics (SPC) for the active comparator product (including any AstraZeneca comparator).

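### For patients still on AZD9291 after the final cut-off, Section 7.8 limits the 28 days after last dose to treatment-related SAEs, while Section 6.3.1 collects all SAEs and all deaths over the same window

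*Supplement*

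**What the plan says.** Two sections of the protocol govern safety data from patients who remain on drug at the end of the study.

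Section 7.8 (Post study access to study treatment) covers this group: "Patients receiving AZD9291 at the time of study completion (i.e. after final data cut-off date) may continue to receive AZD9291". While on drug they are monitored and all safety assessments continue. After stopping they are "followed up for a period of 28 days after the last AZD9291 dose is administered for any new treatment-related serious adverse events". On reporting: "A CSR addendum will be prepared to summarise any additional safety data collected".

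Section 6.3.1 (Time period for collection of adverse events) introduces the same situation: "After the final database lock, there may be some patients remaining on study treatment". For these patients, "AstraZeneca will collect information (during the treatment period and for 28 days after last dose) on SAEs, deaths (including those due to disease progression"), together with discontinuations due to AEs or SAEs and drug accountability. The list is closed by the word only. The general rule earlier in that section is that "SAEs occurring in the follow-up period should be reported to AstraZeneca in the usual manner", with a reference to Section 6.4.

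Section 6.4 states: "All SAEs have to be reported, whether or not considered causally related to the investigational product". Section 8.5 puts every AE within 28 days of the last dose into the AE summaries, whatever its attribution.

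**The concern.** The same window carries two different event scopes. Section 7.8 filters on the investigator's causality judgement; Section 6.3.1 does not. A site reading 7.8 for a patient who stops drug after the cut-off would look only for related SAEs. A site reading 6.3.1 would report every SAE and every death.

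Attribution is a weak filter in this design. The study is single-arm and open-label, so there is no comparator against which to judge background events, and Section 6.8.1 plans no DMC. Section 6.7 shows how hard attribution can be: the work-up for suspected interstitial lung disease has to exclude lymphangitic spread of the cancer, infection and cardiac causes. An event wrongly put down to the disease would not be picked up under 7.8.

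The restriction in 7.8 also adds little scope of its own. Section 6.3.2 already asks investigators to notify the sponsor of any SAE they learn of, at any time, if a causal link to AZD9291 is reasonably possible. At stake are the completeness of the CSR addendum for the period after the last dose, and consistency between sites.

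**Working it through.** No arithmetic applies. The check is a comparison of the texts.

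**1. Are the patients the same?** In substance, yes. Section 7.8 starts at the final data cut-off and Section 6.3.1 at the final database lock. For a patient who stops between those two points, the general rule of 6.3.1 and Table 8 would apply. That rule collects all new AEs up to the 28-day follow-up, so 7.8 is narrower there too.

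**2. Is the window the same?** Yes: 28 days after the last dose in both.

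**3. Is the event scope the same?** No. By type of event in those 28 days:

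| Event | Section 7.8 | Section 6.3.1 |
|---|---|---|
| SAE judged related, including fatal | Collected | Collected |
| Non-fatal SAE judged unrelated | Not collected | Collected |
| Death from an AE judged unrelated | Not collected | Collected |
| Death clearly due to progression | Not collected | Collected |

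The first row includes related deaths because Section 6.2 makes an AE that results in death an SAE. The last row needs care: Section 6.3.10 says that deaths clearly due to progression are not reported as SAEs. Deleting the causality restriction from 7.8 would therefore not bring them in; deaths have to be named separately, as 6.3.1 does.

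**4. Which version do other sections support?** Section 6.4 requires all SAEs regardless of causality. Section 8.5 summarises any AE in the 28-day window. Both agree with 6.3.1, and 7.8 stands alone.

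**5. Is this the current text?** Yes. Neither Amendment 1 nor Amendment 2 revises 6.3.1, 6.4 or 7.8. Amendment 2 does change Section 8.5, but only the ECG baseline.

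**6. The on-treatment period.** Section 7.8 has all safety assessments performed until the drug is stopped. Section 6.3.1 collects only SAEs, deaths, discontinuations due to AEs or SAEs, and drug accountability. The two can be read together if the other assessments are done but not entered in the database. Neither section says so, and the addendum is to summarise whatever is collected.

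**The case against.** The strongest reply is that no event need be lost. Section 6.3.1 addresses these patients directly and sits in the safety-reporting section, whose content the principal investigator must see that all study staff know. Section 7.8 is a paragraph about access to drug. If sites follow 6.3.1, capture is complete. This stands as a limit: the loss is conditional on 7.8 being applied. It does not remove the contradiction, because nothing says which section prevails.

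A second reply is that 6.4 ties part of its duty to SAEs in the course of the study, whereas 7.8 is headed as post-study. That makes 6.4 secondary support. The counter-argument from Section 9.3, which ends the study at the last subject's last visit, is only arguable. The conflict between 7.8 and 6.3.1 does not need 6.4.

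A reader might also infer more than the documents support:

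- **SAE rates would appear to fall with time on drug.** They would not for this reason. Neither section filters SAEs by causality while the patient is on treatment; the filter acts only after the last dose.
- **These patients are the only source of late-toxicity data.** They are not. Under Section 8.1 patients are followed to an updated analysis 12-24 months after the last enrolment, so long exposures are already covered by the ordinary AE rules.
- **The addendum would pool the narrower period with earlier AE rates.** No section says this. Safety summaries are left to the SAP, which is not among the documents, so the lack of a rule on separate presentation is not a finding.
- **Section 7.8 omits all deaths.** It does not: a fatal related AE is an SAE and is covered.

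**Conclusion.** The contradiction is real and stands in the current protocol. For patients who continue beyond the final cut-off or lock, 7.8 and 6.3.1 prescribe different event scopes for the same 28 days. Where 7.8 is followed, SAEs judged unrelated, and unrelated or progression deaths, would be missing from the addendum for that window. A second, softer mismatch concerns which on-treatment safety data are recorded.

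The number of events cannot be estimated. It would need the number of patients still on drug, the SAE and death rates in the 28 days after stopping, the share judged unrelated, and the proportion of sites applying 7.8; the documents give none of these. Modelling how many patients remain on drug from an assumed treatment duration would count patients, not lost events. What can be said is that the exposure is one 28-day window per affected patient.

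ORR, the other efficacy endpoints and the safety summaries up to the final cut-off are untouched. The point is worth correcting because it changes what is collected and the correction costs almost nothing.

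**What to change.** Amend Section 7.8 to the scope of Section 6.3.1: all SAEs and all deaths, regardless of causality, on treatment and for 28 days after the last dose. Name deaths separately, since progression deaths are not SAEs under Section 6.3.10. Use one trigger, either data cut-off or database lock, in both sections.

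Reconcile the two sections on the on-treatment period by stating which assessments named in 7.8 are entered in the database and which are done without being collected.

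The cost is a wording change and a few more SAE reports, which 6.3.1 already calls for.

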8. STATISTICAL ANALYSES BY ASTRAZENECA

8.1 Statistical considerations

A comprehensive Statistical Analysis Plan (SAP) will be prepared prior to first subject enrolled. All Analyses will be performed by AstraZeneca or its representatives. Additional details relating to the Independent Central Review will be detailed in the Independent Central Review Charter.

The data cut-off for the primary analysis of ORR will take place 3 months after the last subject enrolled, to allow opportunity for all patients to complete two RECIST follow-up assessments. At this time, DoR and safety/tolerability will also be summarised. The primary analysis CSR will report the analysis of ORR supported by duration of response, and safety and tolerability data.

The full CSR will report the analysis of all primary and secondary endpoints (including updated ORR and DoR, DCR, tumour shrinkage, PFS, OS, Safety, HRQoL, QTc and PK) and summarise the exploratory endpoint of patient reported adverse events (PRO-CTCAE). The data cut-off for this analysis will take place approximately 8 months after the last subject has been enrolled, to allow responding patients to have a DoR greater than 6 months.

All patients will continue to be followed up for an updated analysis that will occur between 12-24 months after the last patient has been enrolled. All endpoints will be updated and summarised in an addendum to the CSR.

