(a) A total of 175 patients will be treated with AZD9291. Patient enrolment will consist of 2 cohorts: approximately 50 patients with T790M+ NSCLC who have progressed following EGFR-TKI treatment but who have not received further treatment, and approximately 125 patients with T790M- NSCLC who have progressed following minimum prior therapy with an EGFR-TKI and a platinum-based doublet chemotherapy. Patients may have also have received additional lines of treatment.

(b) Patients will be considered enrolled at the time AZD9291 treatment is started. Patients will continue to receive AZD9291 treatment until objective disease progression (according to RECIST 1.1) or for as long as they are receiving clinical benefit in the opinion of the Investigator. Patients who discontinue study treatment for reasons other than disease progression must continue tumour assessments as per the protocol schedule until progression.

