5.1 Efficacy assessments

5.1.1 RECIST 1.1

All imaging assessments including unscheduled visit scans should be collected on an ongoing basis and sent to an AstraZeneca (AZ) appointed Clinical Research Organisation (CRO) to enable independent central analyses.

For both Independent Central Review (ICR) and investigator review RECIST 1.1 criteria will be used to assess each patient's tumour response to treatment and allow calculation of ORR, PFS, DCR, DoR, and assess tumour shrinkage. The RECIST 1.1 guidelines for measurable, non-measurable, target and non-target lesions and the objective tumour response criteria [CR (complete response), PR (partial response), SD (stable disease) or PD (progression of disease)] are presented in [Appendix D](#). For ORR, a visit response of CR or PR must be confirmed by a later scan conducted at least 4 weeks after the initial response is observed. See [Section 4](#) for considerations related to RECIST 1.1 assessments.

The methods used at baseline for assessment of tumour burden [CT or MRI scans of chest and abdomen (including liver and adrenal glands)] must be used at each subsequent follow-up assessment. Any other areas of disease involvement should be additionally investigated based on the signs and symptoms of individual patients. CT/MRI scan of the brain should be performed in patients with known or suspected brain metastases. The baseline assessment should be performed within 28 days of treatment start. Assessments to be performed every 6 weeks relative to first dose until objective disease progression. It is important to follow the assessment schedule as closely as possible. If scans are performed outside of the scheduled visit \pm 1 week window interval and the patient has not progressed, every attempt should be

made to perform the subsequent scans at their scheduled time points. Any other sites at which new disease is suspected should also be appropriately imaged.

If the investigator is in doubt as to whether progression has occurred, particularly with response to non-target lesions (NTLs) or the appearance of a new lesion, it is advisable to continue treatment until the next scheduled assessment or sooner if clinically indicated and reassess the patient's status. If repeat scans confirm progression, then the date of the initial scan should be declared as the date of progression.

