ORR rate is defined as the number (%) of subjects with measurable disease with at least one visit response of CR or PR that is confirmed at least 4 weeks later (according to ICR for the primary analysis). Data obtained up until progression, or last evaluable assessment in the absence of progression, will be included in the assessment of RR. However, any complete response or partial response which occurred after a further anticancer therapy was received will not be included in numerator of the ORR calculation.

In the case where a subject has two non-consecutive visit responses of PR, then, as long as the time between the 2 visits of PR is greater than 4 weeks and there is no PD between the PR visits, the subject will be defined as a responder. Similarly, if a subject has visit responses of CR, NE, CR, then, as long as the time between the 2 visits of CR is greater than 4 weeks, then a best response of CR will be assigned.

Duration of Response (DoR)

Duration of response will be defined as the time from the date of first documented response, (that is subsequently confirmed) until date of documented progression or death in the absence of disease progression, the end of response should coincide with the date of progression or death from any cause used for the PFS endpoint. The time of the initial response will be defined as the latest of the dates contributing towards the first visit response of PR or CR. If the response is not confirmed, it will not be included.

If a subject does not progress following a response, then their duration of response will use the PFS censoring time.

Disease control rate (DCR)

Disease control rate is defined as the percentage of patients who have a BoR of CR or PR or SD.

Tumour Shrinkage

Tumour shrinkage will be assessed using RECIST tumour response. The absolute change and percentage change from baseline in sum of tumour size at each assessment will be calculated. The best change in tumour size will include all assessments prior to progression or start of subsequent anti-cancer therapy.

Progression Free Survival (PFS)

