8.4 Outcome measures for analyses

Previous text:

Progression Free Survival (PFS)

PFS is defined as the time from enrolment until the date of objective disease progression or death (by any cause in the absence of progression) regardless of whether the patient withdraws from study therapy or receives another anti-cancer therapy prior to progression. Patients who have not progressed or died at the time of analysis will be censored at the time of the latest date of assessment from their last evaluable RECIST assessment.

Revised text:

Progression Free Survival (PFS)

PFS is defined as the time from **date of first dose** until the date of objective disease progression or death (by any cause in the absence of progression) regardless of whether the patient withdraws from study therapy or receives another anti-cancer therapy prior to

progression. Patients who have not progressed or died at the time of analysis will be censored at the time of the latest date of assessment from their last evaluable RECIST assessment.

Section of protocol affected:

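### At exactly 8 months after last enrolment, a last-enrolled responder still in response and scanned on schedule is censored at about 5.5 months at most, so the stated aim of DoR above 6 months is not met

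*Supplement*

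**What the plan says.** Protocol Section 8.1 places the full-CSR data cut-off "approximately 8 months after the last subject has been enrolled, to allow responding patients to have a DoR greater than 6 months". The Synopsis (Statistical methods) and Section 8.9.4 give the same reason. Amendment 2 revised the neighbouring paragraph on the 3-month cut-off in all three places and left this sentence alone, so it is current text.

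The rules that decide how much DoR a patient can show are elsewhere:

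- **Clock.** Figure 1, note (b), in Section 1.5: "Patients will be considered enrolled at the time AZD9291 treatment is started". Follow-up and scan schedule start on the same day.
- **Scans.** Section 5.1.1: "Assessments to be performed every 6 weeks relative to first dose until objective disease progression", with a tolerance of one week either side.
- **Start of DoR.** Section 8.4 dates it from the first response that is later confirmed, at the "latest of the dates contributing towards the first visit response of PR or CR".
- **End of DoR, event.** Section 8.4: "the end of response should coincide with the date of progression or death from any cause used for the PFS endpoint".
- **End of DoR, no event.** Section 8.4: "If a subject does not progress following a response, then their duration of response will use the PFS censoring time". In the PFS definition as revised by Amendment 2, such patients are "censored at the time of the latest date of assessment from their last evaluable RECIST assessment".

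Section 8.9.2 reports the number and percentage of responders with DoR above 3, 6, 9 and 12 months, and a Kaplan-Meier plot and median with 95% CI. Section 8.1 plans an update of all endpoints 12 to 24 months after the last enrolment.

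**The concern.** The reason given for the date works only if DoR is counted up to the cut-off. The protocol does not count it that way: an ongoing response stops contributing time at the last evaluable scan. With scans every six weeks, up to six weeks of follow-up before the cut-off adds nothing to an ongoing response, and here the cut-off falls shortly before a scheduled scan.

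Durability is an important support for a response rate in a single-arm trial, and this is the only reason the protocol gives for the 8-month date. In the count of responders above 6 months, a late enrollee who is still responding would fall below the threshold because of scan timing, not because the response ended.

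**Working it through.** **Inputs.** Cut-off 8 months and target 6 months (Section 8.1); scans at weeks 6, 12, ..., 30, 36, 42, each ±7 days (Section 5.1.1); enrolment = first dose (Section 1.5); DoR start and censoring (Section 8.4, with Amendment 2). Days are counted as elapsed since first dose; one month = 365.25/12 = 30.44 days.

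**Thresholds.**
- Cut-off: 8 × 30.44 = 243.5 days (34.8 weeks).
- Target: 6 × 30.44 = 182.6 days (26.1 weeks).

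**The plan's figure.** Counting from response to cut-off:
- Week-6 response: 243.5 − 42 = 201.5 days = 6.6 months. This is the only count found that gives more than 6 months on the nominal schedule.
- Week-12 response: 243.5 − 84 = 159.5 days = 5.2 months, so even this count fails.

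**Under the protocol's censoring rule.** Maximum DoR of an ongoing responder = last scan on or before the cut-off − first response scan. For the last-enrolled patient, week 30 is day 210 and is in; week 36 is day 252 and misses by 252 − 243.5 = 8.5 days.

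| First response | Scans | DoR |
|---|---|---|
| Week 6, on schedule | 210 − 42 | 168 days = 5.5 months |
| Week 6, windows stretched (day 35 to day 217) | 217 − 35 | 182 days = 5.98 months |
| Week 12, on schedule | 210 − 84 | 126 days = 4.1 months |

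The stretched-window case misses by 0.6 day, so it depends on the day-count convention and is effectively at the threshold.

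**Exceptions.**
- A death without progression is dated when it occurs. For a week-6 responder, a death between about day 225 (42 + 182.6) and day 243.5 gives more than 6 and up to 6.6 months.
- Section 8.4 sends unscheduled scans to the central review, so a scan in the same interval would count.
- Eight calendar months span 242 to 245 days. A week-36 scan taken 7 days early (day 245) could fall on the cut-off: 245 − 42 = 203 days = 6.7 months.
- A cut-off at 8.3 months or later takes in the nominal week-36 scan (252/30.44 = 8.28 months).

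**How many patients.** On nominal scans, week-6 responders are affected only if enrolled in the last 8.5 days. Week-12 responders need the week-42 scan (day 294), so they are affected if enrolled in the last 294 − 243.5 = 50.5 days. The documents give no accrual period. Assuming uniform accrual over 6 to 10 months (182.6 to 304.4 days):
- Week-6 responders: 8.5/304.4 to 8.5/182.6 = 3% to 5%.
- Week-12 responders: 50.5/304.4 to 50.5/182.6 = 17% to 28%.

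**With the cut-off at 37 weeks** (day 252 + 7 = 259; 8.5 months):
- Week-6 response: 252 − 42 = 210 days = 6.9 months, so 0% affected.
- Week-12 response: 252 − 84 = 168 days = 5.5 months; (294 − 259) = 35 days, or 12% to 19% under the same accrual assumption.
- Covering week-12 responders needs day 294 to 301, that is 9.7 to 9.9 months.

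**The case against.** The date is stated as approximate, and 8.5 days is a small shift; a cut-off at 8.3 months makes the reason true for a week-6 responder. The sentence does not say all responders or last-enrolled responders, whereas the 3-month paragraph does speak of all patients. Kaplan-Meier estimation handles this kind of administrative censoring, and the 12 to 24 month update closes the gap. No test, decision rule, sample size or primary result depends on the date. The SAP is not among the documents and may hold an operational cut-off rule.

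Most of this stands and limits the size of the point. It does not remove it. Whether the stated purpose is met turns on those 8.5 days, so an unspecified tolerance leaves the answer open. The date is also counted from the last enrolment, which makes the last-enrolled patients the natural test of its reason.

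A reader might infer that no last-enrolled responder can exceed 6 months, or that late-enrolled ongoing responders all stop just short. The documents do not support either. Deaths are dated events, unscheduled scans count, and an early visit or a slightly later cut-off brings in week 36. Week-6 responders enrolled more than about 8.5 days before the last patient can pass 6 months, and last-enrolled week-12 responders, at 4.1 months, are well short, not just short.

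**Conclusion.** The point holds in a limited form. At exactly 8 months and on scheduled scans, a last-enrolled patient still in response has at most about 5.5 months of DoR after a week-6 response and 4.1 months after a week-12 response. The stated reason for the date is therefore not met under the protocol's own censoring rule.

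This rests on a 30.44-day month, no unscheduled scan, and no death without progression before the cut-off. The shares affected (3% to 5% of week-6 responders, 17% to 28% of week-12 responders) also rest on an assumed accrual period. The output at risk is the crude count of responders above 6 months at this one cut-off. The Kaplan-Meier estimates and the primary ORR analysis are not called into question.

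**What to change.** In the Synopsis and Sections 8.1 and 8.9.4, tie the full-CSR cut-off to the last patient's week-36 scan including its window: 37 weeks (about 8.5 months) after the last first dose. State that this gives first-scan responders up to 6.9 months of DoR, and that last-enrolled week-12 responders would need the week-42 scan, at about 9.7 to 9.9 months. The cost is 259 − 243.5 = 15.5 days, about two weeks, on one cut-off.

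If the date must stay, replace the reason with what it delivers: about 5.5 months of DoR follow-up for last-enrolled first-scan responders still in response. That costs one sentence and a less favourable stated figure.
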